- f Prior medications Record all medications taken within 30 days of Screening Visit. Concomitant medications Enter new medications started within 28 days before the first dose of study drug through the Safety Follow-up Visit. Record all medications taken for AEs.
- g AEs and laboratory safety measurements will be graded per NCI CTCAE v5.0. All AEs, whether gradable by CTCAE or not, will also be evaluated for seriousness. The Week 3 AE review can be captured via telephone; no visit is required.
- h Record all AEs occurring within 30 days after the last dose of study drug. Report all SAEs (related and unrelated to study drug) and ECIs occurring up until 90 days after the last dose of study drug or 30 days after the start of new anticancer treatment, whichever comes first. Afterwards, report only SAEs and ECIs that are related to study drug.
- i Vital signs include temperature, pulse, respiratory rate, weight, and blood pressure. Height will be measured at Visit 1 only.
- j ECOG Performance Status and laboratory tests for screening are to be performed within 10 days prior to the first dose of study drug.
- k ECGs should be performed on Day 1, Day 3, and Day 5 of each cycle. ECGs should be performed in triplicate approximately 5 minutes apart at each time point assessed. ECGs will be obtained predose of pembrolizumab on Cycle 2 Day 1. ECGs should also be obtained predose of ALKS 4230, at the end of infusion, and 1 hour (±15 minutes) after the completion of administration of ALKS 4230.
-  A pregnancy test (urine or serum) must be given to all women of childbearing potential before each treatment cycle begins. Pregnancy test results must be confirmed as negative before Dose 1 of each cycle is administered for all cycles.
- m Coagulation factors (PT/INR and aPTT) should be tested as part of the screening procedures and before collection of the post-treatment (second) biopsy for all patients. Any patient receiving anticoagulant therapy should have coagulation factors monitored closely throughout the study.
- n After Cycle 1, laboratory samples can be collected up to 72 hours prior to Day 1 (CBC with differential; complete serum chemistry panel, including magnesium, calcium, and phosphorus; and urinalysis). CBC and complete serum chemistry panel should also be done up to 72 hours prior to Day 1 of the ALKS 4230 infusion.

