# **13.5.** Safety and Tolerability Analyses

Safety will be evaluated based on the occurrence of AEs, vital signs, results of clinical laboratory tests, and ECG findings. Reported AE terms will be coded using the Medical Dictionary for Regulatory Activities (MedDRA®) version 21 preferred terms and system organ classes.

Treatment-emergent AEs (TEAEs) are defined as any AE that begins on or after the first administration of the study drug. Adverse event severity will be graded according to the CTCAE v5.0 and terms recorded on the CRFs will be mapped to preferred terms using the most recent version of the Medical Dictionary for Drug Regulatory Activities (MedDRA).

All AEs will be listed. The incidence of TEAEs will be summarized for each group and overall, by severity, and by relationship to study drug as assessed by the Investigator. The summary tables will include the number and percentage of patients with TEAEs overall, by system organ class, and by preferred terms within each system organ class. Similar tables will be prepared for SAEs, TEAEs leading to discontinuation, as well as additional categories of AEs as defined in the SAP.

Results of clinical laboratory tests will be summarized by visit for the absolute value and for change from baseline. Tables showing the shift from baseline will also be presented.

ECG findings will be listed.

Concomitant medications will be categorized and presented using the World Health Organization Anatomical Therapeutic Chemical (WHO-ATC) drug classification system.

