3.13.2. Adverse Events

Analyses of AEs will include only "treatment-emergent" AEs (TEAEs). TEAEs are defined as any AE that begins on or after the first administration of the study drug. Events where the onset date was the same as the study drug start date will be assumed to be treatment-emergent, unless the study drug start time and the AE start time are collected, and the AE start time is prior to the study drug start time. If an incomplete onset date is collected for an AE, the AE will be assumed to be treatment-emergent unless there is evidence that confirms that the AE was not treatmentemergent (eg, the AE end date is prior to the date of the first dose of study drug). No imputation will be performed for partial dates for AE. Analyses will not include those that have an onset greater than 30 days after study drug discontinuation.

Treatment-related AEs reported beyond 30 days after study drug discontinuation will be summarized separately during post treatment discontinuation period.

TEAEs will be summarized by Preferred Term (PT) within a System Organ Class (SOC) according to the Medical Dictionary for Regulatory Activities (MedDRA) version 21.0 or higher.

Patients reporting more than one AE within a SOC will be counted only once for that SOC. Patients reporting the same AE more than once will be counted only once for that PT. For summaries of TEAEs by the National Cancer Institute Common Terminology Criteria for Adverse Events (NCI CTCAE 5.0) grade, at each level of summation each patient is counted only once at the maximum grade level. The possible grade levels are 1 to 5, and unknown. If a patient had an AE with unknown grade, then the patient will be counted in the grade category of "unknown," even if the patient had another occurrence of the same event with a grade of 1 or 2. If the patient had another occurrence of the same AE with a grade of 3, 4 or 5, the patient will be counted under the grade 3, 4 or 5 categories based on the maximum grade level reported.

The number and percentage of patients experiencing at least one TEAE will be further summarized as follows.

- Any TEAE
- Any TEAE experienced by $\geq 10\%$ of patients
- Any TEAE with NCI CTCAE toxicity \geq Grade 3
- Any TEAE broken down by maximum NCI CTCAE toxicity grade (severity)
- Any TEAE related to ALKS 4230 as assessed by the Investigator
- Any TEAE related to pembrolizumab as assessed by the Investigator

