- Any TEAE with NCI CTCAE toxicity ≥Grade 3 and related to ALKS 4230 as assessed by the Investigator
- Any TEAE with NCI CTCAE toxicity ≥Grade 3 and related to pembrolizumab as assessed by the Investigator
- Any Treatment Emergent Serious Adverse Event (SAE)
- Any SAE related to ALKS 4230 as assessed by the Investigator
- Any SAE related to pembrolizumab as assessed by the Investigator
- Any SAE related to ALKS 4230 with NCI CTCAE
 Grade 3 as assessed by the Investigator
- Any SAE related to pembrolizumab with NCI CTCAE > Grade 3 as assessed by the Investigator
- Any TEAE leading to discontinuation of ALKS 4230
- Any TEAE leading to dose interruption of ALKS 4230
- Any TEAE leading to dose reduction of ALKS 4230
- Any TEAE leading to discontinuation of pembrolizumab
- Any TEAE leading to death

The tables will be sorted by overall descending frequency of SOC and then, within a SOC, by overall descending frequency of PT based on the patient count for the overall column.

The original date and time will be shown on all listings of AEs. Listings will be provided for all TEAEs, serious TEAEs, and TEAEs leading to study treatment discontinuation. The data listings will be provided for dose reductions, and dose interruptions along with the AE/SAE that was associated with the change in dosing for ALKS 4230 and pembrolizumab separately.

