5. CHANGES IN CONDUCT OR PLANNED ANALYSES FROM THE PROTOCOL

There are no changes made to the statistical methods specified in the ION-01-ALKS 4230 study protocol (dated 29 Dec 2018).

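### Non-fatal SAEs judged unrelated, with onset 31 to 90 days after stopping, fall in no adverse-event table of the SAP, provided the protocol's 90-day collection window stands

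*SAP*

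**What the plan says.** **Analysis.** SAP 3.13.2 restricts adverse-event analyses to treatment-emergent events (TEAEs), which it defines by a start on or after first dose with no end date. It then adds: "Analyses will not include those that have an onset greater than 30 days after study drug discontinuation". For later events it provides one output: "Treatment-related AEs reported beyond 30 days after study drug discontinuation will be summarized separately during post treatment discontinuation period". The general SAE row in that section is for treatment-emergent SAEs; every other SAE row requires a relationship to ALKS 4230 or pembrolizumab.

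**Collection.** Protocol Table 4, footnote h: "Report all SAEs (related and unrelated to study drug) and ECIs occurring up until 90 days after the last dose of study drug", or until 30 days after new anticancer treatment begins if that is sooner. Table 5 tracks AEs to 90 days after discontinuation in all four patient categories, or to 30 days after discontinuation if new therapy begins. Protocol 12.4 differs: after the Safety Follow-up Visit it collects only events the investigator thinks may be related, while also sending the reader to Table 5 for long-term collection.

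**Protocol analysis plan.** Protocol 13.5: "Treatment-emergent AEs (TEAEs) are defined as any AE that begins on or after the first administration of the study drug". It promises corresponding tables for SAEs and a listing of all AEs, with no 30-day limit on either.

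**Declared changes.** SAP Section 5: "There are no changes made to the statistical methods specified in the ION-01-ALKS 4230 study protocol". SAP 5.1 lists one revised definition, the Efficacy Evaluable Population.

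**The concern.** The protocol asks sites to report SAEs whatever their cause for up to three months after treatment, but the SAP tabulates the last two of those months only for events judged treatment-related. In an open-label, single-arm study, whether a late SAE counts towards incidence then rests on the causality judgement of an investigator who knows the treatment. Tabulating SAEs regardless of attribution guards against that, and the protocol already requires the data.

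Safety and tolerability of the combination is a secondary objective (Protocol 6.2). Protocol 12.3.1 warns that immune-related events can appear months after the last pembrolizumab dose, so the period after day 30 matters. The cap also narrows the analysis in Protocol 13.5 without being declared, so a reader who relies on SAP Section 5 would not know of it.

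**Working it through.** The plan states no figure to reproduce. The check sets the two windows side by side and traces one event through the planned outputs. Days are counted from the last dose, taking last dose and discontinuation as the same day.

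1. **Maximum gap.** Collection of SAEs regardless of relationship runs to day 90 (footnote h, Table 5). AE analyses stop at day 30 (SAP 3.13.2). Gap = 90 − 30 = 60 days, that is days 31 to 90; 60/90 = 66.7% of the maximum window. This is a share of calendar time, not of events.

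2. **Effect of new anticancer therapy.** If it starts on day d, footnote h ends collection on day min(90, d + 30), so the gap is min(60, d) days. For d = 15, collection ends on day 45 and the gap is 15 days; for d = 60 or later it is the full 60 days. Under Table 5, collection for such a patient ends on day 30 and the gap is 0. The two protocol rules differ.

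3. **Effect of Protocol 12.4.** Table 4 places the Safety Follow-up Visit at 30 ± 5 days, so between days 25 and 35. If 12.4 governs and means that visit, unrelated events are collected to day 35 at the latest and the gap is at most 35 − 30 = 5 days. Table 5 also names a Safety Follow-up Visit at 90 days for patients who progress on study. If 12.4 means that visit for them, their gap is again up to 60 days.

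4. **Tracing one event.** Take a non-fatal SAE on day 50, judged unrelated, with no new therapy started.
   - Collected: yes under footnote h and Table 5; under 12.4, not if the 30-day visit is meant.
   - General TEAE and SAE tables: excluded by the 30-day sentence.
   - Related-SAE tables and the post-discontinuation summary: excluded, because it is not related.
   - Death listings (SAP 3.13.3): not applicable.
   - Listing of serious TEAEs (SAP 3.13.2): unclear. The event meets the open-ended TEAE definition, and the SAP does not say whether the cap on analyses covers listings.
   - Result: no table counts it; a listing may show it.

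5. **Declaration.** SAP 5.1 has one entry, and it is not the cap.

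6. **Anchor.** Footnote h counts from the last dose and SAP 3.13.2 from study drug discontinuation. SAP 3.13.2 has separate rows for discontinuing ALKS 4230 and discontinuing pembrolizumab, but does not say which date starts the 30 days when they differ.

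7. **Events affected.** Neither document gives an SAE rate for any period, so this cannot be calculated.

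**The case against.** The strongest objection is that the SAP may simply follow Protocol 12.4. All events to about 30 days and only related ones afterwards is close to that section's rule, and if it governs, almost nothing collected goes untabulated. This stands as a condition on the point. It does not remove it: footnote h and Table 5 both say 90 days, and 12.4 itself refers to Table 5.

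A reader might also infer that these events disappear from the report. The documents do not support that. The SAP's TEAE definition is open-ended, the 30-day sentence limits analyses rather than the definition, and Protocol 13.5 says all AEs will be listed. The SAP does state for its Grade 3-or-higher laboratory listings (3.13.4) that no time limit applies, and says nothing similar for AE listings, so the matter is open. A listing also gives no incidence.

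Nor is late immune toxicity as such lost. An event judged related stays in the separate summary. The protocol's causality scale allows a possibly related rating even when another cause is equally likely, and Protocol 12.5 groups possible with probable and definite relationship. Only events rated below that leave the tables. Many progression events are in any case exempt from SAE reporting (Protocol 12.5.1).

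Events of clinical interest are not lost either. The one criterion shown, the hepatic laboratory one, is counted and listed under SAP 3.13.4 with no time or relationship limit stated.

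**Conclusion.** The point holds for tables, and conditionally. If the protocol's 90-day window stands, non-fatal SAEs judged unrelated with onset on days 31 to 90 are collected but counted in no AE or SAE table, and the SAP does not declare the cap. The gap is at most 60 of 90 days, shorter or absent once new anticancer therapy starts, and at most 5 days if Protocol 12.4 governs and means the 30-day visit.

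Two stronger readings should be left aside. One puts a percentage of patients on the loss; with no SAE rate in the documents, any such figure would be invented. The other says the loss falls mainly on patients who stopped early for toxicity; nothing in the documents shows this.

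The primary efficacy result is untouched. The change is still worth making, because it costs little and stops the reported incidence of late SAEs from depending on an unblinded causality judgement.

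**What to change.** 1. Reconcile Protocol 12.4 with Table 4 footnote h and Table 5, including their different wording for patients who start new therapy, so that there is one SAE collection window for the SAP to follow.
2. In SAP 3.13.2, keep the 30-day limit for the main TEAE tables.
3. Add one table of all SAEs regardless of relationship, from first dose to the end of the reconciled window, split at 30 days after the last dose of whichever study drug was stopped later.
4. State that the SAE listing is not capped at 30 days.
5. Declare the 30-day cap in SAP 5.1 as a departure from Protocol 13.5, and amend the no-change statement in Section 5.

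No separate table for events of clinical interest is needed beyond the laboratory summary in SAP 3.13.4.

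The cost is a few SAP sentences and one extra table from data that footnote h already requires, plus the protocol clarification in item 1. Reported SAE incidence may rise slightly; showing the two periods separately keeps the 30-day figure available for comparison.

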3.13.3. Death

Listings will be provided for patients who died during the study for any reason, and for patients who had died due to AE.

3.13.4. Clinical Laboratory Parameters

Laboratory parameters will be presented in conventional (ie, US) units. Only scheduled laboratory parameters, as specified in Table 1, will be included in the laboratory results summaries, unless specified otherwise. All laboratory data, including those collected at unscheduled visits, will be included in the listings.

For all quantitative parameters listed in Table 1, the actual value and the change from baseline to each postbaseline visit will be summarized by visit using descriptive statistics. Only data collected as scheduled will be included in the summaries. For each parameter, the mean (+/- SE) at each scheduled visit will be plotted for its actual value and its change from baseline. Data collected at the EOS/ET visit will be included as one time point regardless of subjects' EOS status.

In addition, where applicable, hematology and chemistry laboratory determinations will be categorized according to NCI CTCAE (version 5) grades and shifts from baseline NCI CTCAE grades to maximum and final post-baseline grades will be assessed. The baseline and final grades will be defined respectively as the grade of the last measurement collected prior to the first dose of study drug, and as the last post-baseline measurement collected no more than 30 days after the last dose of study drug.

The maximum NCI CTCAE toxicity grade value will be the value with the highest NCI CTCAE toxicity grade collected after the first dose of study drug and within 30 days following study drug discontinuation. In cases where multiple values are collected on the same day, the maximum grade value will be selected as the value for that day.

The number and percentage of patients with baseline grades versus maximum post-baseline grades of and baseline grades versus final post-baseline grades will be summarized.

Detailed listings of data for subjects experiencing NCI CTCAE grade \geq 3 hematology and chemistry values will be provided. All measurements collected, regardless of the number of days after study drug discontinuation will be included in these listings.

Pregnancy test data will be listed.

Number of subjects who meet protocol defined event of clinical interest criteria (Section 12.1.1 of protocol) as below will be summarized and corresponding listing will be presented.

• An elevated aspartate aminotransferase or alanine aminotransferase laboratory value that is $\geq 3 \times$ the upper limit of normal (ULN) and an elevated total bilirubin laboratory value that is $\geq 2 \times$ ULN and an alkaline phosphatase laboratory value that is $< 2 \times$ ULN.

For urinalysis, the number of abnormalities at any post-baseline visit will be summarized.

Hematology	Chemistry	Urinalysis	Other
 Haematocrit Haemoglobin Red blood cell count (RBC) Total white blood cell count (WBC) Platelet count Differential blood count including: Basophils Eosinophils Neutrophils Lymphocyte Monocyte 	 Sodium Potassium Phosphorus Glucose Total protein BUN Serum creatinine CrCl Albumin Total bilirubin ALT AST LDH ALK-P CO₂ or bicarbonate^a Uric acid Calcium Chloride Magnesium Direct bilirubin, if total bilirubin is elevated above the upper limit of normal 	 Specific gravity Protein pH Glucose Ketones Blood Microscopic examination of sediment, only if urinalysis dipstick results are abnormal (2+ or higher) Urine pregnancy test^b 	 Serum β-hCGb PT (INR) aPTT TSH Cortisol (morning) ACTH

 Table 1:
 Clinical Laboratory Assessments

Abbreviations: ACTH=adrenocorticotropic hormone; ALK-P=alkaline phosphatase; ALT=alanine a minotransferase; ANC=absolute neutrophil count; a PTT=activated partial thromboplastin time; AST=aspartate aminotransferase; BUN=blood urea nitrogen; CBC=complete blood count; CO₂=carbon dioxide; CrCl=creatinine clearance; hCG=human chorionic gonadotropin; INR=international normalized ratio; LDH=lactic dehydrogenase;

PT=prothrombin time; TSH=thyroid-stimulating hormone.

a If considered standard of care in local region.

b Perform on women of childbearing potential

3.13.5. Vital Signs

Vital signs assessments include respiratory rate, temperature, blood pressure, and heart rate. The observed values at each visit and change from baseline to post-baseline visits will be summarized with descriptive statistics. All vital sign data will be presented in the patient data listings.

Patients who meet PCS criteria will be summarized for vital signs parameters.

The figure of mean (+/- SE) of the change from baseline will be summarized by visit for systolic blood pressure, diastolic blood pressure, heart rate and temperature.

3.13.6. Electrocardiograms (ECG)

ECG parameters (heart rate, RR interval, PR interval, QRS interval, QT interval will be summarized for each visit during the study. QT interval changes from baseline will also be descriptively summarized for each visit. The baseline value will be taken as the average of the triplicate ECG measurements taken prior to the first dose on Cycle 1 Day 1.

The number and percent of patients with abnormal ECG findings at any postbaseline visit will be summarized.

Individual ECG evaluation results will be provided in data listings. A supportive listing will present all values for a parameter for patients with abnormal ECG results.

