ICH	International Conference on Harmonization
ICU	Intensive Care Unit
IFN	Interferon
IL-2	Interleukin-2
IL-2R	Interleukin-2 Receptor
INR	International Normalized Ratio
ir	Immune-Related
irORR	Immune-Response Overall Response Rate
irRC	Immune-Related Response Criteria
IV	Intravenous or Intravenously
LDH	Lactate Dehydrogenase
λ_z	Terminal Elimination Rate Constant
MAX	Maximum
MEDDRA	Medical Dictionary for Regulatory Activities
MIN	Minimum
MTD	Maximum Tolerated Dose

Abbreviation	Definition
NCI	National Cancer Institute
NK	Natural Killer [Cells]
N/A	Not Applicable
ORR	Overall Response Rate
PCS	Potentially Clinically Significant
PD	Progressive Disease
PD-1	Programmed Death Receptor-1
PD-L1	Programmed Death Ligand-1
PFS	Progression-Free Survival
PR	Partial Response
РТ	Preferred Term
PTT	Partial Thromboplastin Time
Q3W	Every 3 Weeks
QTCF	QT Interval Corrected by The Fridericia Correction Formula
RCC	Renal Cell Carcinoma
R _{CD8}	Ratio of Cd8 Cells To T _{regs} (Day 1 Pre-Infusion As Baseline Levels)
R _{CD8, max}	Maximum R _{CD8}
RECIST	Response Evaluation Criteria in Solid Tumors
iRECIST	Immune Response Evaluation Criteria in Solid Tumors
R _{NK}	Ratio of Nk Cells to T _{regs} (Day 1 Pre-Infusion As Baseline Levels)
R _{NK, max}	Maximum R _{NK}
RP	Relative Percentage
RP2D	Recommended Phase 2 Dose
SAE	Serious Adverse Event
SAP	Statistical Analysis Plan
SD	Stable Disease
SE	Standard Error
SI	Standard International System of Units
SOC	System Organ Class
SOP	Standard Operating Procedure

Abbreviation	Definition
T _{1/2}	Terminal Elimination Half-Life
TEAE	Treatment-Emergent Adverse Event
TLF	Table, Listing and Figure
T _{MAX}	Time to C _{max}
TNF	Tumor Necrosis Factor
T _{CD8, MAX}	Time to Maximum R _{CD8}
T _{NK, MAX}	Time to Maximum R _{NK}
TT _{REGS}	Regulatory T Cells
TSH	Thyroid-Stimulating Hormone
ULN	Upper Limit of Normal
US	United States
VS	Versus
V _{SS}	Steady-State Volume of Distribution
Vz	Terminal Volume of Distribution
WHO	World Health Organization

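### SAP 3.13.6 summarises QT without heart-rate correction, so a change in heart rate between baseline and later ECGs can attenuate or hide QTc prolongation

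*SAP*

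**What the plan says.** SAP 3.13.6 lists the parameters: "ECG parameters (heart rate, RR interval, PR interval, QRS interval, QT interval will be summarized for each visit during the study". It then gives one change-from-baseline analysis: "QT interval changes from baseline will also be descriptively summarized for each visit". The reference is a predose value: "The baseline value will be taken as the average of the triplicate ECG measurements taken prior to the first dose on Cycle 1 Day 1". Nothing in the section says how triplicates after baseline are combined.

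The SAP abbreviation list contains an entry for QTcF, "QT Interval Corrected by The Fridericia Correction Formula", but no analysis section of the SAP or protocol refers to it again, and no QTc threshold is given.

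The other ECG outputs in SAP 3.13.6 are a count, "The number and percent of patients with abnormal ECG findings at any postbaseline visit will be summarized", and listings: "Individual ECG evaluation results will be provided in data listings". The protocol promises less. Its Section 13.5 says only "ECG findings will be listed".

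On collection, footnote k to protocol Table 4 says "ECGs should be performed in triplicate approximately 5 minutes apart at each time point assessed". It asks for ECGs on Days 1, 3 and 5 of every cycle, with ALKS 4230 time points before dosing, at the end of infusion and 1 hour later. The ECG row of Table 4 itself marks only screening, Week 1 and end of treatment.

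**The concern.** Raw QT shortens as heart rate rises, whatever the state of repolarisation. A change in raw QT can be read as a drug effect only if heart rate is about the same at both measurements.

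There is reason to doubt that here. Protocol 8.4.2 requires antipyretic premedication to lessen infusion-related fever or chills, and protocol 8.3.5 warns of infusion-type reactions with ALKS 4230, naming cytokine release syndrome among the types. Footnote k places ECGs at the end of infusion and 1 hour later, while the baseline is a predose average. The study has no control arm against which a shift common to all patients could be judged.

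At stake is the interpretation of a safety table. ECG findings are a named safety assessment (protocol Section 12) and safety is a secondary objective (protocol 6.2). A mean fall in QT in the planned table could coexist with a real rise in QTcF. If heart rate fell instead, the error would run the other way.

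**Working it through.** The documents state no QT or QTc figure, so there is nothing to reproduce. The check asks how far a heart-rate change can move raw QT.

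**Inputs from the documents.** The analysed variable is uncorrected QT, the baseline is the predose C1D1 triplicate average (both SAP 3.13.6), and the correction named is Fridericia (SAP abbreviations).

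**Assumptions, not in the documents.** Baseline heart rate is 70 bpm (range 65 to 80). Baseline QTcF is 410 ms (range 390 to 430). The heart-rate rise is 10, 20 or 30 bpm, and the true QTcF rise is 0 or 30 ms.

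**Formulas.** QTcF = QT / RR^(1/3), with RR = 60/HR in seconds, so QT = QTcF × (60/HR)^(1/3). The QTcF rise that leaves raw QT unchanged is QTcF₀ × [(HR₁/HR₀)^(1/3) − 1].

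**Baseline.** QT = 410 × (60/70)^(1/3) = 389.5 ms.

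**Later value when QTcF truly rises from 410 to 440 ms:**
- 80 bpm: 440 × (60/80)^(1/3) = 399.8 ms, change +10.3 ms
- 90 bpm: 440 × (60/90)^(1/3) = 384.4 ms, change −5.1 ms
- 100 bpm: 440 × (60/100)^(1/3) = 371.1 ms, change −18.4 ms

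**Results from 70 bpm and 410 ms:**

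| Heart-rate rise | Raw QT change, no true QTcF change | Raw QT change, true QTcF rise of 30 ms | QTcF rise at which raw QT change is zero |
|---|---|---|---|
| 10 bpm | −17.0 ms | +10.3 ms | 18.7 ms |
| 20 bpm | −31.3 ms | −5.1 ms | 35.8 ms |
| 30 bpm | −43.7 ms | −18.4 ms | 51.8 ms |

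**Sensitivity to baseline heart rate (65 to 80 bpm, QTcF 410 ms).** A true 30 ms rise appears as +9.3 to +11.9 ms for a rise of 10 bpm, −7.4 to −1.4 ms for 20 bpm, and −21.7 to −13.0 ms for 30 bpm. The break-even QTcF rises are 16.4 to 20.0, 31.7 to 38.4 and 45.9 to 55.3 ms.

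**Sensitivity to baseline QTcF (390 to 430 ms, 70 bpm).** The break-even rises are 17.8 to 19.6, 34.1 to 37.6 and 49.2 to 54.3 ms.

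The attenuation is present throughout. Whether the sign reverses depends on the size of the heart-rate rise.

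**Which ECGs reach the table.** SAP 6.1 keeps one value per scheduled visit and does not say which. Protocol Table 4 note a makes Day 1 before dosing the general default. The Table 4 row and footnote k disagree on which ECGs are done. The documents therefore do not settle whether end-of-infusion and 1-hour tracings enter the by-visit summary.

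**The case against.** The strongest reply is that no passage states or quantifies a faster heart rate after ALKS 4230. The protocol speaks of a potential for fever or chills and mandates antipyretics to reduce it. It does not say when fever would occur relative to the post-infusion ECGs. This stands: the heart-rate step is an inference. A reader might take the protocol to expect tachycardia, and so conclude that the planned table will conceal prolongation. The documents support only that it can.

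Second, if predose values fill the by-visit table, acute infusion effects matter much less to it. This also stands in part. But then the end-of-infusion and 1-hour ECGs have no stated place in the by-visit summary, which is a gap of its own.

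Third, there are other safeguards. SAP 3.13.6 summarises heart rate and RR beside QT, counts abnormal ECGs and lists individual results. SAP 3.13.5 plots heart-rate and temperature changes. A clinically significant ECG change could be reported as an adverse event. These help, so it would be too strong to say that the ECG safety question goes unanswered. But separate group summaries of heart rate do not correct QT within a patient, the abnormal count has no QTc criterion, and listings leave the correction to the reader.

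Fourth, the parenthesis in the parameter list is never closed, so an item may have been lost. The sentence that follows is complete and names only the QT interval.

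Finally, the protocol commits only to listing ECG findings, the analysis is descriptive, and the documents describe no QT signal. This limits the weight of the point but does not make raw QT the right variable.

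**Conclusion.** The point holds in this form: the planned change-from-baseline summary uses raw QT, and any heart-rate difference from baseline will distort it. On the assumed 70 bpm and 410 ms, a true 30 ms QTcF rise shrinks to about +10 ms with a 10 bpm rise, and turns to about −5 and −18 ms with rises of 20 and 30 bpm. These figures illustrate the mechanism. They do not predict what this trial will show.

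The conclusion rests on the Fridericia relation, on the assumed heart rates and QTcF, and on heart rate differing between the tracings compared. It does not show that ALKS 4230 prolongs QT or raises heart rate. Efficacy results are unaffected. The change should be made before database lock.

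**What to change.** In SAP 3.13.6:
- Derive QTcF = QT/RR^(1/3), with RR in seconds, for each tracing. Average the triplicates at each time point, post-baseline as well as baseline.
- Make QTcF and its change from baseline the primary QT summary, by visit and by time relative to infusion (predose, end of infusion, 1 hour after). Write an exception to the one-value-per-visit rule in SAP 6.1; without it, a QTcF table could still omit the post-infusion ECGs.
- Add counts of patients by maximum QTcF and by maximum increase, with cut-points stated in the SAP before lock.
- Keep raw QT in the listings.

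The sponsor should also reconcile the ECG row of protocol Table 4 with footnote k, because together they determine which tracings exist.

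The cost is SAP wording, one derived variable and some extra table programming. No new procedure is needed if QT and RR (or heart rate) are recorded for each tracing. The documents do not include the eCRF, so this should be confirmed.
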